9.2 Setting

Patients with FD who are receiving ERT and their caregivers will be identified and recruited from approximately 8-12 specialist centres across four countries (Taiwan, Turkey, Brazil and Japan). The number of sites needed to achieve the required sample size may vary between the participating countries; this will be determined by the study management company (in consultation with Amicus Therapeutics), depending on the number and size of potentially

eligible study sites in each country. It is anticipated that 2-3 sites will be required in each country.

The participating centres will be specialist hospitals or treatment centres with experience of treating patients with FD with ERT (agalsidase alfa or agalsidase beta or both), interest in taking part in the study and likely availability of the required number of eligible patients/ERT episodes during the recruitment period.

In some of the participating countries, the preparation and administration of ERT takes place exclusively in the hospital setting; in these countries the study will be conducted solely within the hospitals (or infusion centres affiliated to the hospitals) from which the patients and caregivers are recruited. In other countries, ERT preparation and administration can take place in both hospitals and community healthcare centres (i.e. primary care treatment facilities). In these countries, patients who receive ERT in primary care (and their caregivers) will still be identified and recruited from their main (specialist) hospital, but the time and motion component of the study (observation of ERT preparation and administration) and distribution of patient- and caregiver- reported outcome measures and questionnaires will take place at their community healthcare centre (from which the relevant approvals to conduct the study will also be obtained). In some cases, patients may attend their community healthcare centre for the ERT infusion to be set up, and return home to start/deliver the infusion; these patients (and their caregivers) will still be included in the study, and the total HCP/patient and caregiver time recorded as for other episodes while the patient attends the community healthcare centre. Patients will capture the infusion time themselves by completing the bespoke questionnaire provided.

It is not routine practice in the countries of study for ERT preparation and administration to take place exclusively in the home setting, or for HCPs to attend the patient's home to assist with the infusion, although this may occur in exceptional circumstances (for example, if the patient themselves is a trained HCP). For this reason, patients who prepare and administer their ERT exclusively in the home setting will be excluded from the study, as resource use is likely to be atypical.

9.3 Study time periods

It is anticipated that the prospective recruitment / data collection period for this study will be approximately 4-5 months, starting from the date on which the relevant approvals to conduct the study are in place. Ideally, a maximum of two episodes of care per patient during the data collection period will be included for the time and motion evaluation (except in exceptional cases where it is determined that it is required to observe three episodes per patient due to a limited number of available patients/episodes for observation). Patients with FD and their caregivers will be asked to complete the study questionnaires once during the data collection period, when the patient attends the hospital or treatment centre for administration of ERT; the exception is the work productivity questionnaire, which will be completed on two occasions and the bespoke Fatigue Likert scale, which will be completed on three occasions (as described above). Separate patient consents will be obtained for the time and motion evaluation and cross-sectional questionnaire completion so patients will have the option to take part in only one or both parts of the study, according to their preference.

9.4 Study population

The source population for this study is adult patients with FD, recruited from four countries (Taiwan, Turkey, Brazil and Japan) who attend the participating hospitals, treatment centres or community healthcare facilities for administration of ERT (as part of their routine treatment) during the data collection period, and their caregivers. It is anticipated that approximately 60 episodes of care (30 with agalsidase alfa and 30 with agalsidase beta) per country, ideally up to a maximum of two episodes per patient (except in exceptional cases where it is determined that it is required to observe three episodes per patient due to a limited number of available patients/episodes for observation), will be included in the time and motion study, and approximately 30 sets of patient questionnaires and 5 sets of caregiver questionnaires per country (in total) will be completed.

Patients and caregivers fulfilling the following criteria will be eligible for inclusion in the study:

9.4.1 Selection criteria for patients

Patient inclusion criteria

- Patients aged 18 years old or over at time of consent.

- Patients with a documented diagnosis of FD.
- Patients who have received ≥4 doses of ERT (with agalsidase alfa or agalsidase beta) for the treatment of FD.
- Patients who present to the participating hospital(s) or treatment centre(s) for administration of a dose of ERT (as part of their routine treatment) during the data collection period.

Patients who meet any of the following criteria will be excluded:

- Patients aged <18 years at time of consent
- Patients who are unable or unwilling to give consent for study participation.
- Patients for whom ERT preparation and administration takes place exclusively in the home setting.
- *For the time and motion evaluation:* Patients whose ERT is administered by a HCP who does not consent to be observed.

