Setting	Patients with FD who are receiving ERT and their caregivers will be identified and recruited from approximately 12 specialist centres in four countries (Taiwan, Turkey, Brazil and Japan).
Participants	
The target sample size for the time and motion evaluation undertaken as part of this study is 240 ERT episodes, including 60 ERT episodes (30 for agalsidase alfa and 30 for agalsidase beta) in each participating country. Ideally, a maximum of two ERT administration episodes will be observed per patient; as such, at least 30 patients are expected to be enrolled in each country. For countries with limited FD patient numbers, a review of episodes of care observed will be completed on an ongoing basis. It may be determined that it is possible to observe three episodes per patient in these circumstances, however only two episodes will be observed per patient wherever possible.
 
For the questionnaire evaluation, approximately 120 patients and 20 caregivers will be expected to fill questionnaire sets (approximately 30 patients' and 5 caregivers' questionnaire sets per country).
 
Patient inclusion criteria
 
 • Patients aged 18 years old or over at time of consent. • Patients with a documented diagnosis of FD. • Patients who have received ≥ 4 doses of ERT (with agalsidase alfa or agalsidase beta) for the treatment of FD. • Patients who present to the participating hospital(s) or treatment centre(s) for administration of a dose of ERT (as part of their routine treatment) during the data collection period.

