
Summary measures of (at date of consent, unless specified):
 
 • Sex. • Age at onset of first symptoms, at FD diagnosis and at date of consent. • Duration of ERT treatment. • ERT treatment. • FD phenotype (organs involved). • FD mutation ((if known)). • Severity of FD (to be determined using the specified baseline information]). • Any other relatives (with whom the patient lives) with FD. • Number and type (agalsidase alfa / agalsidase beta) of ERT infusions received in the year prior to date of enrolment. 	
 • Sex (male / female). • Date of consent. • Age at consent. • Age at onset of first symptoms. • Date of FD diagnosis. • ERT start date. • ERT treatment under observation (agalsidase alfa / agalsidase beta). • Number of ERT infusions received in the year prior to date of enrolment, by type of treatment (agalsidase alfa, agalsidase beta). • FD phenotype (organ involvement/complications), to include any current or prior history of: hypohidrosis, neuropathic pain (and/or acroparesthesia and/or acute pain crises), cornea verticillata, angiokeratomas, hearing impairment (including deafness and/or tinnitus), cardiac events (including rhythm and/or conduction disturbances, hypertrophic cardiomyopathy or left ventricular mass index [LVMi] above normal range, myocardial infarction

	
[MI], unstable angina, congestive heart failure, major cardiac medical procedures), renal events (including reduced estimated glomerular filtration rate [eGFR], abnormal albumin creatinine ratio [ACR], proteinuria or albuminuria, dialysis, kidney transplant), central nervous system (CNS) involvement (including brain magnetic resonance imaging [MRI] changes [white matter lesions], transient ischaemic attack [TIA] or stroke), FD-related gastrointestinal [GI] symptoms, plasma lyso-Gb3 levels above normal, low white blood cells (WBC) alpha-galactosidase, other: specify)
 
• eGFR at enrolment (closest measurement prior and preferably within 12 months); date and measurement.• Urine protein levels at enrolment (closest measurement prior); date and measurement.• WBC alpha-galactosidase (closest prior to enrolment); date and measurement• LVMi at enrolment (closest measurement prior and preferably within 12 months); date and measurement.
--	---

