9.8 Study size

This study aims to recruit sufficient patients to record 30 episodes per treatment per country. Given this, the number of patients recruited will range from 15 to 30 per treatment per country. To evaluate the value of the sample estimates of the population that this sample size will allow for, it will be assumed pessimistically that each patient will have one measurement; the estimates once the study is carried out will therefore have higher precision than calculated below.

The anticipated length of time for pre and post-administration activities and infusion for each treatment utilised estimates from the research of Guest et al.¹⁷ alongside clinical opinion sourced from sites in the countries of study; it was estimated that pre-administration processes would always take between 10-30 minutes, post-administration processes would take between 15-30 minutes, infusion of agalsidase alfa takes between 40 to 60 minutes and infusion of agalsidase beta would take between 90 to 180 minutes. To anticipate the precision of estimates given the sample size above, it was estimated that these times would follow a normal distribution within these ranges (as a result, the mean could be estimated by taking the middle value of the range and the standard deviation roughly approximated accordingly).

It is important to account for the fact that Fabry disease is rare and that the sample collected will represent a large proportion of the total population with disease. For instance, in the US, it was estimated that there were only approximately 7700 patients in total out of a population of about 323 million in 2016, which suggests that only 0.0024% have the disease. The estimated number of Fabry disease patients in other countries can be calculated from the prevalence of the disease in the US, by multiplying the expected proportion of the population with the disease (assuming that the prevalence is similar in the US to other countries) with the estimated total population (Brazil, Japan, Taiwan and Turkey therefore could have an estimated patient population of about 5015, 3033, 573 and 1934 patients respectively based on estimates of total population of 210 million, 127 million, 24 million and 81 million patients respectively²⁴). Accounting for this, the estimated precision of estimates of time at different sample sizes for the largest and smallest countries in the study by population can be seen in the table below.

Table 5. Sample size estimations

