9.11 Limitations of the research methods

- Patient and caregiver consent is a requirement of this study; this may introduce selection bias and result in a study sample that may not be representative of the wider patient and caregiver population of interest.
- Centres will be selected on the basis of interest in taking part in the study and experience in treating patients with FD with ERT. It is acknowledged that these centres may not be representative of current wider clinical practice in the countries of study.
- For patient- and caregiver-reported outcomes, the data will rely on the completeness of the answers provided by participants, which will not be queried or otherwise followed up to clarify inconsistencies or omissions and may be subject to reporting bias.
- A limitation of asking patients to complete questionnaires during their ERT infusion is that they may feel more anxious and/or tired when they are attending the hospital to receive treatment than at other times; consequently, the descriptions of patient-

reported HRQoL and general wellbeing obtained in the study may be an overestimate of the overall impact of FD.

- This is a descriptive study and no analyses to control for confounding will be carried out. For ethical reasons, time and motion data will not be stratified by individual staff member, although the performance of staff may be a factor in any observed variability. Experience levels of staff performing tasks observed in the study may vary between centres and may not reflect the experience level of staff performing the same tasks outside the study centres. There are also likely to be differences between the participating countries in local clinical protocols, healthcare settings and care processes, which may introduce variability in the data collected.
- It is acknowledged that the time and motion evaluation may not capture the full burden of ERT administration since first infusions (which are expected to take longer than subsequent infusions) are excluded from the study; this is because the longer first infusion represents only a one-off burden at the start of long-term (potentially lifelong) treatment.
- It is also acknowledged that QoL data could be impacted by ERT episodes that are close in timing to each other.

10. Other aspects

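### The four-dose run-in is not tied to the product observed, so the first infusion after a product switch can enter the new product's primary summary

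*Protocol*

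**What the plan says.** The run-in rule in Protocol section 9.4.1 is "Patients who have received ≥4 doses of ERT (with agalsidase alfa or agalsidase beta) for the treatment of FD". The abstract repeats it. Neither place says that the doses must be of the product given at the observed visit, and no exclusion criterion mentions a change of product.

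The primary endpoint is total HCP time for one dose, summarised by country and by product (Protocol section 9.6, Table 4; SAP section 2.6). On the target per cell, section 9.8 says: "This study aims to recruit sufficient patients to record 30 episodes per treatment per country".

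Section 9.11 states that "first infusions (which are expected to take longer than subsequent infusions) are excluded from the study". The reason it gives is that "the longer first infusion represents only a one-off burden at the start of long-term (potentially lifelong) treatment".

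Table 4 records the product given at each episode, a single ERT start date, and the number of infusions of each product in the year before enrolment. Neither document uses these items to screen patients or to remove episodes. SAP sections 2.1 and 2.3 contain no episode-level exclusion, and Protocol section 9.9.4 plans no sensitivity analysis.

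**The concern.** The criterion counts ERT experience as a whole, while the result is reported for each product. Someone established on one product who changes to the other already satisfies the criterion at the first infusion of the new one. Recruitment is consecutive (section 9.5), so such a patient would be enrolled if they consented, and the episode would be counted in the new product's cell.

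If that infusion takes more staff time than a settled one, the cell mean no longer describes routine infusions of that product. Each cell has only 30 episodes, so a few unusual ones can move it. The rationale in section 7 says the data may go to health technology assessment bodies, where the product-specific means are likely to be read closely.

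**Working it through.** **1. Can a post-switch first infusion enter the primary summary?**

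- Eligibility (abstract and 9.4.1): at least four doses, either product. A switcher passes at dose one of the new product.
- Exclusions (same sections): age, consent, treatment exclusively at home, and HCP refusal to be observed. None applies.
- Analysis (SAP 2.1, 2.3, 2.6): all episodes with data are summarised by country and product. None is removed for treatment history.
- Data items (Table 4): the prior-year counts by product stop at enrolment. The product recorded at each episode would show a change between two observed visits, but not how many doses of the new product had been given. The ERT start date is not stated to be by product.

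So the episode can enter, and the planned data identify it only in part.

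**2. Yardstick: reproducing Table 5 (Brazil, 30 patients)**

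Inputs from section 9.8: pre-administration 10 to 30 minutes, post-administration 15 to 30 minutes, "infusion of agalsidase alfa takes between 40 to 60 minutes", "infusion of agalsidase beta would take between 90 to 180 minutes", and an estimated N = 5015 patients in Brazil. The table reproduces when each SD is taken as range/4 and the component SDs are added:

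- Alfa SD = 5 + 3.75 + 5 = 13.75 minutes
- Beta SD = 5 + 3.75 + 22.5 = 31.25 minutes
- Half-width = t(0.975, 29) × SD/√30 × √((5015 − 30)/(5015 − 1))
- Overall Alfa: 5.12 minutes, giving 87m23 to 97m37, as printed (92m30 − 87m23 = 5m07)
- Overall Beta: 11.64 minutes, giving 165m52 to 189m08, as printed (177m30 − 165m52 = 11m38)

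**3. Illustrative shift in a cell mean**

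The documents give neither the number of recent switchers nor the extra time of a post-switch infusion. Assume k of the 30 episodes are such infusions, each with d extra minutes of HCP time. The shift is k × d / 30:

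| k | d = 30 | d = 60 | d = 90 |
|---|---|---|---|
| 0 | 0 | 0 | 0 |
| 1 | 1 | 2 | 3 |
| 2 | 2 | 4 | 6 |
| 3 | 3 | 6 | 9 |

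For k = 1 to 3 the range is 1 to 9 minutes. Against the half-widths that is 1/5.12 to 9/5.12, about 0.2 to 1.8, for Overall Alfa, and 1/11.64 to 9/11.64, about 0.1 to 0.8, for Overall Beta. Table 5 adds infusion time to pre- and post-administration time, so it gives only a rough scale for HCP time.

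**The case against.** A reader might infer that 9.4.1 contradicts 9.11. The documents do not support this. Section 9.11 does not define first infusions, and its reason refers to the beginning of long-term treatment, which reads naturally as the start of ERT. On that reading the four-dose rule delivers the exclusion in full. The two sections conflict only if first means first of each product, which is nowhere written.

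A reader might also infer that the product-specific means are biased upward. That too goes beyond the text:

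- Nothing says that the first infusion of the other product takes longer in a patient already used to ERT.
- No switching rate is given.
- Table 4 times the infusion separately from HCP administration and monitoring, so a longer infusion need not add staff time minute for minute.
- A switcher observed two or three times gives at most one first infusion of the new product. Applying the full excess to the later episodes has no basis in 9.11.
- The prior-year counts by product show that mixed histories can be recorded, not that post-switch first doses are expected in the sample.

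Keeping switchers in could also be a deliberate choice, since section 9.1 stresses broad eligibility and routine practice, and no treatment comparison is planned.

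These points remove the claims of contradiction and of demonstrated bias. They do not close the gap: the endpoint is by product, the run-in is not, and the plan does not say which meaning of first infusions it intends.

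**Conclusion.** The gap is real and its effect is unknown. The run-in does not secure four prior doses of the product whose HCP time is being summarised, and nothing later in the plan makes up for that.

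The illustrative shift of 1 to 9 minutes rests wholly on two assumptions: 1 to 3 post-switch first infusions in a cell of 30, and 30 to 90 extra minutes of HCP time at each. At the upper end it would exceed the Table 5 half-width for Overall Alfa and stay below that for Overall Beta. If no recent switcher presents, or if such infusions need no extra staff time, it is zero. Table 5 and the targets of 30 episodes are unaffected. This is a low-cost improvement to the design, not an error in a stated figure.

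**What to change.** 1. **Protocol 9.4.1 and abstract.** For the time and motion component only, require that the four or more prior doses be of the product being observed (agalsidase alfa or agalsidase beta). The section already has one criterion confined to that component, so the form exists. Leave questionnaire eligibility unchanged: consent for it is separate, and the length of first infusions is no reason to restrict it.
2. **Table 4 and CRF.** At each observed episode, record the dose number, or the date of the first dose, of the current product. The prior-year count cannot do this, because it stops at enrolment.
3. **Protocol 9.11.** Make the wording on first infusions match, so that it states whether first of ERT or first of the product is meant.
4. **SAP 2.6.** State that episodes not meeting the requirement are left out of the primary product-specific summary and listed separately.

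The cost is one extra data item and a few lines of text. A few switchers may be lost from the time and motion sample. With fortnightly dosing, four doses of the new product take about 4 × 2 = 8 weeks of a 4 to 5 month recruitment period, so a patient who switches late may not qualify before recruitment closes.

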9.4.2 Selection criteria for caregivers

Caregiver inclusion criteria:

- Aged 18 years of age or over at time of consent.
- Self-identifies as a caregiver of a patient with FD for whom written informed consent has been obtained for inclusion in the study.

Caregivers who meet any of the following criteria will be excluded:

- Caregiver (and/or the patient with FD whom they support or care for) is unable or unwilling to give consent for study participation.

9.4.3 Selection criteria for staff (for time and motion study)

Staff inclusion criteria (for time and motion study):

- Members of the whole care team responsible for preparing and administering agalsidase alfa and agalsidase beta to patients with FD.
- Staff who have given written consent to be observed during the preparation and provision of care.

9.5 Patient identification, sampling and recruitment

Adult patients with FD who are receiving treatment with ERT will be identified from local databases and pharmacy records by members of the whole care team at each centre and assessed for eligibility in line with the inclusion criteria. Patients will be approached by a member of their care team, given information about the study and invited to consent to participate. Patients may be approached in advance of their next scheduled attendance for ERT administration (by telephone and/or post) or in person, at a routine hospital visit. If patients do not wish to complete the study questionnaires they are still eligible for the time and motion study (and vice versa), provided that consent for the relevant component of the study has been obtained. For patients who are eligible to be observed more than once (for the time and motion study), initial consent for observation of up to three episodes of care will be obtained, and will be confirmed verbally by their HCP before the second and third episode of care. Each patient will only be asked to complete one set of questionnaires (with the exception of the work productivity questionnaire, which will be completed twice and the bespoke Fatigue Likert scale, which will be completed three times), even if they contribute more than one episode of care to the time and motion study.

Caregivers will only be invited to participate in the study if the patient whom they care for also consents to study participation. Caregivers will be approached for consent when they attend the hospital or treatment centre with the patient for their ERT administration visit.

Consecutive eligible patients (and their caregivers) presenting at the participating centres during the prospective recruitment period will be included in the study until the required sample size is reached. It is anticipated that patient and caregiver recruitment will take place over a 4-5 month period, starting from the date on which the relevant approvals needed to conduct the study are in place.

Prior to commencement of data collection, HCPs at the participating centres (and community healthcare facilities, where relevant) who are involved in the administration of ERT will be identified and asked to provide consent to be observed in their provision of care. Consent from HCPs will be confirmed by the observer verbally before each episode of care.

